6.5.6 ECOG performance status

Performance status will be determined using the ECOG performance status scale (see **Table 4**). Wherever possible, the patient's performance status should always be assessed by the same personnel throughout the study.

Table 4. ECOG performance status scale.

Grade	Scale
0	Fully active, able to carry on all pre-disease performance without restriction.
1	Restricted in physically strenuous activity but ambulatory and able to carry out work of a light or sedentary nature, i.e., light housework, office work.
2	Ambulatory and capable of all selfcare but unable to carry out any work activities. Up and about more than 50% of waking hours.
3	Capable of only limited selfcare, confined to bed or chair more than 50% of waking hours.
4	Completely disabled. Cannot carry on any selfcare. Totally confined to bed or chair.
5	Dead.

http://www.ecog.org/general/perf_stat.html

6.6 Tumor and blood samples

All patients will be required to provide a pre-treatment tumor tissue sample and blood samples during screening, and a tumor biopsy sample and a blood sample on Day 15 (+ 1-2 days) at the end of study treatment.

6.6.1 Tumor tissue samples

Mandatory biopsy samples will be collected before the start of treatment (up to a maximum of 8 weeks before the first dose of study drug). If a diagnostic biopsy was performed maximum 8 weeks prior to initiation of study treatment, it can be used as a baseline sample for the Ki67 assessment. Additional biopsy will be taken at the EoT (+ 1 day) after the last dose of study drug.

Note: if post-treatment biopsy cannot be obtained within + 1 day from last day of treatment (on D15 or D15+1), treatment will be extended to 16 days and patients will be able to have surgery or biopsy the following day (be it D15 + 2 days).

Tumor samples obtained are to be collected as tumor paraffin embedded block (two formalin fixed paraffin-embedded blocks [FFPE]). Tumor tissue samples must be of good quality based on total and viable tumor content: Samples must contain a minimum of 500 viable tumor cells that preserve cellular context and tissue architecture. Samples collected via resection, core-needle biopsy (at least three cores, embedded in a single paraffin block), punch, or forceps biopsy are acceptable.

Note: Details regarding Ki67 staining can be found in the separate laboratory manual.

Note II: Samples must contain a minimum of 500 viable tumor cells. In the event of containing less cells (but as long as there's a minimum of 350 viable cells), the case can be discussed with the medical monitor and a second FFPE block can be sent to the Sponsor's designated central laboratory.

These samples will be used for assessing study co-primary endpoints referring to changes in tumor cell proliferation as measured by Ki67 expression between baseline and day 15 post-treatment tumor biopsy samples by central assessment in patients with centrally confirmed Ki67 $\geq 10\%$ (Arm A vs Arm B), and other secondary endpoints as indicated in the protocol.

6.6.2 Blood samples

Mandatory liquid biopsies will be taken before the start of study treatment (up to a maximum 14 days before the first dose of the study drug) and, if possible, at the same timepoint as baseline hematological laboratory assessments, and at the EoT (+ 1 day after the last dose of study drug, which will be D15, D15+1, D16+1). Post-study treatment liquid biopsy samples will be taken at the same timepoint, if possible, as post-study treatment tumor biopsies.

These samples will be used to perform a plasma endocrine panel with samples pre- and post-therapy. Please refer to the study laboratory manual for more information.

Since the identification of new markers that correlate with disease activity and the efficacy or safety of treatment is rapidly developing, the definitive list of analyses remains to be determined.

6.7 Patient discontinuation

Patients have the right to withdraw from the study at any time for any reason. The investigator also has the right to withdraw patients from the study in the event of intercurrent illness, AEs, and treatment failure after a prescribed procedure, protocol violation, administrative reasons, or for other reasons. An excessive rate of withdrawals can render the study uninterpretable; therefore, unnecessary withdrawal of patients should be avoided.

Should a patient decide to withdraw, all efforts should be made to complete and report the observations as thoroughly as possible. Although the patient has no obligation to provide the reasons for his/her voluntary withdrawal, the investigator should contact the patient or a responsible relative by telephone or through a personal visit to establish as completely as possible the reason for the withdrawal.

A complete final evaluation at the time of the patient's discontinuation from the study should be made. The principal specific reason for the removal of a patient from the study must be clearly stated in his/her medical records and will be recorded on the CRF.

In the case that the patient decides to prematurely discontinue study treatment, he/she should be asked if he/she can still be contacted for further information. The outcome of that discussion should be documented in both the medical records and in the CRF.

6.8 Study and site discontinuation

The Sponsor reserves the right to terminate this study at any time. Reasons for terminating the study may include, but are not limited to, the following:

- The incidence or seriousness of AEs in this or other studies indicates a potential health risk to patients.
- Patient enrollment is unsatisfactory.
- Data recording is inaccurate or incomplete.
- Excessively slow recruitment.
- Poor protocol adherence.
- Non-compliance with the International Conference on Harmonization (ICH) guideline for Good Clinical Practice (GCP).

7 SAFETY DEFINITIONS AND REPORTING REQUIREMENTS

Safety assessments will consist of monitoring and recording protocol-defined AEs, SAEs and non-serious adverse events of special interest (AESIs); measurement of protocol-specified hematology, clinical chemistry, measurement of protocol-specified vital signs; and other protocol-specified tests that are deemed critical to the safety evaluation of the study drug(s).

7.1 AEs definition

An AE is any untoward medical occurrence in a clinical study subject/patient administered a pharmaceutical product, which does not necessarily have a causal relationship with his/her treatment. An AE can therefore be any unfavorable and/or unintended sign (including an abnormal laboratory finding), symptom or disease temporally associated with the use of a medicinal (investigational) product, regardless of whether it is considered related to the medicinal (investigational) product.

The causal relationship between an AE and the IMP will be defined as below:

Not related: The temporal association between the adverse event and the IMP makes a causal relationship unlikely, or the subject/patient's clinical state or the study procedure/conditions provide a sufficient explanation for the adverse event.

Related: The temporal association between the adverse event and the IMP makes a causal relationship possible and the subject/patient's clinical state or the study procedure/conditions do not provide a sufficient explanation for the adverse event.

Each AE must be assessed by the investigator as to whether or not there is a reasonable possibility of causal relationship to the IMP drugs.

The descriptions and grading scales found in the revised NCI-CTCAE v 5.0 will be utilized for all toxicity reporting. A copy of the CTCAE v 5.0 can be downloaded from the CTEP website (https://ctep.cancer.gov/protocoldevelopment/electronic_applications/docs/ctcae_v5_quick_reference_5x7.pdf).

The intensity (severity) of an AE will be recorded as one of the following but also CTCAE Grade will be recorded:

- Mild - Easily tolerated and does not interfere with normal daily activities, CTCAE Grade 1.
- Moderate - Causes some interference with daily activities, intervention or treatment may be needed. CTCAE Grade 2.
- Severe - Normal daily activities are substantially impaired, hospitalization and/or intervention or treatment is required, CTCAE Grade 3 or 4.
- Fatal - Death, CTCAE Grade 5.

- Not applicable (clinically significant and asymptomatic laboratory test abnormalities or abnormal assessments, for which no CTCAE grading guidance is applicable but which are considered as AEs).

A mild, moderate or severe AE may or may not be serious (see definition below). These terms are used to describe the intensity of a specific AE. However, a severe AE (such as severe headache) may be of relatively minor medical significance and is not necessarily serious. For example, nausea lasting several hours may be rated as severe, but may not be clinically serious. Fever of 39°C that is not considered severe may become serious if it prolongs hospital discharge by a day. Seriousness rather than severity serves as a guide for defining regulatory reporting obligations.

7.1.1 SAEs definitions

Per definition, a SAE is defined as any adverse event that either:

- results in death (i.e., the AE actually causes or leads to death),
- is life threatening (i.e., the AE, in the view of the investigator, places the subject/patient at immediate risk of death when it occurs),
- requires inpatient hospitalization or prolongation of existing hospitalization,
- results in persistent or significant disability/incapacity (disability is defined as a substantial disruption of a person ability to conduct normal life functions),
- is a congenital anomaly/birth defect (in a neonate/infant born to a mother exposed to the investigational product(s)).

7.1.1.1 Definition of life threatening

An AE is life threatening if the subject/patient was at immediate risk of death from the event as it occurred, i.e. does not include an event that might have caused death if it had occurred in a more serious form. For instance, drug induced hepatitis that resolved without evidence of hepatic failure would not be considered life threatening even though drug-induced hepatitis can be fatal.

7.1.1.2 Definition of hospitalization

AEs requiring hospitalization should be considered serious. In general, hospitalization signifies that the subject/patient has been detained (usually involving an overnight stay) at the hospital or emergency ward for observation and/or treatment which would not have been appropriate at the study site. When in doubt as to whether hospitalization occurred or was necessary, the AE should be considered as serious.

Hospitalization for elective surgery or routine clinical procedures, which are not the result of an AE, need not to be notified according to immediate reporting criteria. If anything untoward is reported during any procedure, this must be reported as an AE and either 'serious' or 'non-serious' attributed according to the usual criteria.

7.1.1.3 Definition of clinically/medically significant event

Important medical events that may not result in death, be life-threatening, or require hospitalization may be considered a SAE when, based upon appropriate medical judgment, they may jeopardize the subject/patient and may require medical or surgical intervention to prevent one of the outcomes listed in this definition. Examples of such medical events include allergic bronchospasm requiring intensive treatment in an emergency room or at home, blood dyscrasias or convulsions that do not result in inpatient hospitalization, or the development of drug dependency or drug abuse.

Clinically/medically significant events **MUST** be reported as SAEs.

In this clinical trial and as defined in this protocol, SAEs and hospitalizations unequivocally and solely related to established tumor disease progression will **NOT** be treated as SAEs for reporting obligations.

SAEs, if brought to the attention of the Investigator at any time after the cessation of the study treatment and considered by the Investigator to be possibly related to the study treatment (so, in fact serious adverse reactions), will be reported to the Sponsor.

7.1.1.4 Cases of overdose, medication error, drug abuse, or drug misuse

Overdose (accidental or intentional), medication error, drug abuse, and drug misuse (hereafter collectively referred to as "special situations") are defined as follows:

- Accidental overdose: accidental administration of a drug in a quantity that is higher than the assigned dose.
- Intentional overdose: intentional administration of a drug in a quantity that is higher than the assigned dose.
- Medication error: accidental deviation in the administration of a drug, including accidentally omitted doses. In some cases, a medication error may be intercepted prior to administration of the drug.
- Drug abuse: intentional excessive use of a drug that may lead to addiction or dependence, physical harm, and/or psychological harm.
- Drug misuse: intentional deviation in the administration of a drug that does not qualify as drug abuse. In cases where drug is to be self-administered by the participant, drug misuse could involve the drug being administered to someone other than the participant.

Special situations are not in themselves AEs but may result in AEs. Each AE associated with a special situation should be recorded separately on the Adverse Event eCRF. If the associated adverse event fulfills seriousness criteria or qualifies as an adverse event of special interest, the event should be reported to the Sponsor immediately (i.e., no more than 24 hours after the investigator becomes aware of the event). As an example, an accidental overdose that resulted in a headache would require two entries on the Adverse Event eCRF, one entry to report the

accidental overdose and one entry to report the headache. The "Accidental overdose" and "Medication error" boxes would need to be checked for both entries.

In the event of an overdose, the investigator should follow the steps described in **Section 5.6**.

7.1.2 AESIs for IMPs

AESIs must be reported by the Investigator to the Sponsor expeditiously (see **Section 7.2.1 for reporting instructions**), regardless of their seriousness (i.e., no more than 24 hours after learning of the event). AESIs for giredestrant are as follows:

- Cases of potential drug-induced liver injury that include an elevated ALT or AST in combination with either an elevated bilirubin or clinical jaundice, as defined by Hy's Law (see **Table 5. Guidelines for Management of Patients Who Experience Adverse Events Associated with Giredestrant (GDC-9545)** in **Section 7.2**).
- Suspected transmission of an infectious agent by the study treatment, as defined below:
 Any organism, virus, or infectious particle (e.g., prion protein transmitting transmissible spongiform encephalopathy), pathogenic or non-pathogenic, is considered an infectious agent. A transmission of an infectious agent may be suspected from clinical symptoms or laboratory findings that indicate an infection in a patient exposed to a medicinal product. This term applies only when a contamination of the study drug is suspected.
- Grade ≥ 3 hepatitis or elevations in AST or ALT.
- Grade ≥ 3 acute kidney injury, creatinine increases, or renal toxicity.
- Grade ≥ 2 bradycardia.
- Grade ≥ 2 thromboembolic events.

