In the SOFT and TEXT trials, AI plus OFS was compared to tamoxifen plus OFS in premenopausal women. In a combined updated analysis of these trials, at 12 and 13 years of median follow-up, a statistically significant 17% reduction of distant metastasis was observed, favoring AI with OFS ($P = 0.03$). However, overall survival did not significantly differ between the two clinical trials (Francis, 2019; Francis et al., 2015). A recent meta-analysis comparing AI plus OFS or tamoxifen treatment in premenopausal women shows that AI plus OFS reduces the risk of breast cancer recurrence rather than tamoxifen, especially in patients with high-risk, without breast cancer mortality reduction (Bradley et al., 2022). In addition, for patients with high-risk node-positive EBC, the addition of the cyclin-dependent kinase 4/6 inhibitor (CDK4/6i) abemaciclib to ET for 2 years in the adjuvant setting significantly improved invasive disease-free survival (IDFS) of patients (Johnston et al., 2020).

However, these treatments are associated with short- and long-term side effects that determine the discontinuation of treatment. Class side-effects of AIs are musculoskeletal symptoms, osteoporosis and bone fractures (Bradley et al., 2022; Breast International Group (BIG) 1-98 Collaborative Group et al., 2005; Ea, 2007; Howell et al., 2005) while those of tamoxifen are thromboembolic disease and endometrial cancer (Fisher et al., 1998). OFS worsens tolerance and side effects to adjuvant ET due to induced early menopause. On the other hand, abemaciclib has been associated with diarrhea, fatigue, neutropenia, leucopenia, and nausea (Rugo et al., 2021).

In 2002, fulvestrant became the first-generation selective estrogen-receptor degraders (SERDs) to be used in advanced and metastatic BC (Osborne et al., 2002). SERDs have the potential to completely downregulate estrogen signaling by binding to, blocking and degrading Ers. In EBC, fulvestrant research was limited by the modest benefits over AI in advanced BC. However, preoperative studies provided consistent superiority in inhibition of the cell proliferation, defined by Ki67 marker, over tamoxifen in premenopausal patients (Dowsett, Nicholson, et al., 2005; Young et al., 2008).

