5 STUDY DRUG INFORMATION

The investigational medicinal products (IMPs) for this study are giredestrant (GDC-9545) and tamoxifen.

Complete description of the IMP will be documented in its respective Investigator Brochure (IB) and summary of product characteristics (SmPC), located in the Site/Investigator's file. Summarized information is reported in this section.

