7.2.1 AEs and SAE reporting and timeframe

Reporting requirements will comply with all EU safety reporting requirements as detailed in "Regulation (EU) No 536/2014 of the European Parliament and of the Council of 16 April 2014 on clinical trials on medicinal products for human use, repealing Directive 2001/20/EC".

The investigator is responsible for ensuring that all adverse events (see Section 7.1 for definition) are recorded on the Adverse Event eCRF and reported to the Sponsor in accordance with instructions provided in this section.

For each adverse event recorded on the Adverse Event eCRF, the investigator will make an assessment of seriousness, severity and causality.

During the study period, resolution of adverse events (with dates) should be documented on the Adverse Event eCRF and in the patient's medical record to facilitate source data verification.

The investigator or investigator's team will report all protocol defined SAEs and AESIs to the Sponsor (MEDSIR) no later than 24 hours of any site study team staff becoming aware of the event as follows:

- The full details of the SAE and/or AESI should be collected and fully documented using the SAE form and sent to MEDSIR.
- Follow-up information, copies of the results of any tests, the outcome of the event plus the investigator's opinion of IMP relationship to the SAE(s) and AESI(s), and other document when requested and applicable, will accompany the SAE form as available on the day of reporting or provided as soon as possible thereafter.
- The original SAE Report Form and the fax confirmation sheet from the Sponsor must be kept with the CRF documentation at the study site(s).

All SAE forms will be sent by the investigator or investigator's team to the Sponsor (MEDSIR) according to the reporting instructions provided by MEDSIR at the site initiation visit and filed in the Investigator's File.

All SAEs must be reported to Drug Safety Evaluation (DSE) Clinical Safety and Pharmacovigilance (CSPV) team address: [contact].

SAEs and AESIS will be followed until resolved, a stable outcome or baseline condition is reached, subject/patient is lost to follow-up or dies.

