4.5.2 Adverse Events

The adverse events will be tabulated per arm containing the number and percentage of subjects with the following:

- Subjects with at least one Adverse Event; and number of reported adverse events
- Subjects with at least one AE of special interest (AESI); and number of AESI
- Subjects with at least one Serious Adverse Events (SAEs); and number of SAEs
- Subjects with at least one AE related to the treatment; and number of AE related to the treatment
- Subjects with at least one SAE related to the treatment; and number of SAE related to the treatment

- Subjects who died due to SAEs; and number of SAEs that caused death
- Subjects that dropout due to SAEs; and number of SAEs that caused discontinuation
- Subjects with at least one treatment-emergent adverse event (TEAE); and number of reported TEAE. Adverse events starting or worsening during treatment phase will be considered as TEAEs.
- Subjects with at least one TEAE Grade ≥ 3 ; and number of reported TEAE Grade ≥ 3 .

The AEs will be also summarized according to the primary SOC and within each SOC, by PT according to the Medical Dictionary for Regulatory Activities (MedDRA). The duration of AE will be calculated as follows:

- Duration of an AE (days): (*date of resolution*) – (*start date*) + 1 when both end and start dates of AE are known and complete.

Missing data imputation methods

When data is not completed it will be considered as:

- Day 15 if day is missing
- Day 1 and month July if day and month are missing

In the event of not being able to allocate an AE, it will be considered as being a TEAE. Any missing information will be considered as being the worst case scenario (serious and treatment related).

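### The only AESI list is labelled for giredestrant and its scope for tamoxifen is not stated, yet AESIs are to be shown per arm with no derivation rule, so the two counts are not comparable

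*Protocol*

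**What the plan says.** Protocol section 5 makes both drugs investigational products: "The investigational medicinal products (IMPs) for this study are giredestrant (GDC-9545) and tamoxifen". The AESI section carries a plural heading, "7.1.2 AESIs for IMPs", but its single list is introduced by "AESIs for giredestrant are as follows". No second list follows for tamoxifen, and no sentence there or in the SAP extends the first list to Arm B.

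The list names event types: potential drug-induced liver injury meeting Hy's Law, suspected transmission of an infectious agent, Grade 3 or higher hepatitis or transaminase rise, Grade 3 or higher renal events, Grade 2 or higher bradycardia, and "Grade ≥ 2 thromboembolic events". Protocol 1.2 describes the class side effects of aromatase inhibitors, "while those of tamoxifen are thromboembolic disease and endometrial cancer".

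On reporting, Protocol 7.1.2 sets a 24-hour clock for AESIs whether or not they are serious. Section 7.2.1 repeats this for both categories: the site "will report all protocol defined SAEs and AESIs to the Sponsor" within 24 hours.

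On analysis, Protocol 8.8 and SAP 4.5 say that safety measures, AESIs among them, are described in each arm. SAP 2.5 lists AESI incidence as a safety endpoint. SAP 4.5.2 includes a per-arm row: "Subjects with at least one AE of special interest (AESI); and number of AESI". The SAP contains no AESI definition and no rule for building the flag, and its section 6 declares no change from the protocol.

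**The concern.** A per-arm table invites the reader to compare arms. That works only if a patient with a given event is counted in the same way whichever drug she took. Here the definition is tied by its label to one drug, while the table has a column for each.

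The trial is open-label, so the site knows the arm when it decides whether an event is an AESI. If sites follow the label, they flag events on giredestrant and not on tamoxifen. If sites differ, the tamoxifen count reflects site interpretation. An apparent excess on giredestrant could then come from the definition and not from the drug. Thromboembolism shows the problem most clearly: it is on the list labelled for giredestrant, and the protocol's own background ties it to the comparator.

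**Working it through.** The documents state no AESI rate, count or test, so there is no figure to reproduce. The check is mainly textual.

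**Step 1. What is the scope of the list?**
- For the narrow reading (giredestrant only): the introductory line names giredestrant, and the liver-injury item refers to Table 5, whose title covers events associated with giredestrant.
- For the wide reading (both arms): the section heading is plural. The items are event types with no drug named. One item refers to study treatment in general: "Suspected transmission of an infectious agent by the study treatment, as defined below". Section 7.2.1 has no arm restriction.
- Section 7.2.1 does not settle the matter. It requires reporting of protocol-defined AESIs, and the only definition is the list whose scope is in doubt.

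Both readings can be defended from the text, so the scope is undetermined.

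**Step 2. Does the SAP resolve it?** No. It uses the term in sections 2.5, 4.5 and 4.5.2 without defining it, and does not say whether the row comes from a site flag or from a programmed rule.

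**Step 3. What does the row then show?** Inputs: 46 patients per arm (Protocol 8.1 and 8.2); a true rate r of any listed event, assumed equal in both arms; and a fraction f of qualifying tamoxifen patients whom sites actually flag. Neither r nor f is in the documents; both are assumptions.

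Expected giredestrant patients with an AESI = 46 × r. Expected tamoxifen patients = 46 × r × f.

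| r (assumed) | Giredestrant | Tamoxifen, f = 0 (literal) | Tamoxifen, f = 0.5 | Tamoxifen, f = 1 (list covers both arms) |
|---|---|---|---|---|
| 2% | 46 × 0.02 = 0.92 | 0 | 0.46 | 0.92 |
| 5% | 46 × 0.05 = 2.3 | 0 | 1.15 | 2.3 |
| 10% | 46 × 0.10 = 4.6 | 0 | 2.3 | 4.6 |

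The zero column is an input, not a finding. The table shows only that, with no true difference, the tamoxifen count moves between zero and the giredestrant count according to f, which the plan leaves open.

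**Step 4. What would a literal zero look like?** SAP 4.1 names Clopper-Pearson intervals for binary endpoints. If one were attached to 0 of 46, the upper 95% limit would be 1 − 0.025^(1/46) = 0.077, or 7.7%. It would read as evidence about tamoxifen although no event could have been counted. The SAP does not say that this row will carry an interval, so this is an illustration. The safety set is also analysed by treatment received, so the denominator may not be exactly 46.

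**Step 5. Are the data there to build the flag equally?** Largely yes. Protocol 7.2 requires every adverse event to be recorded, with no distinction by arm, and section 7.1 requires CTCAE grading. Appendix 1 schedules transaminases, bilirubin, alkaline phosphatase and creatinine at the same visits in both arms. The Hy's Law thresholds under Table 5 are stated in laboratory terms that can be applied to either arm. The infectious-agent item is the exception: it depends on the investigator having recorded the suspicion.

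**The case against.** The strongest reply is that the damage is limited and the wide reading is reasonable. The heading, the event-type wording, the reference to study treatment and the unrestricted reporting rule could all lead a site to flag the same events on tamoxifen. The safety analysis is descriptive, with no planned AESI test. All adverse events are summarised per arm by system organ class and preferred term, so a reader could check an apparent excess against those tables. Which events deserve special interest for a comparator is also the sponsor's judgement.

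Much of this stands, and it rules out several stronger conclusions that a reader might draw:

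- *The tamoxifen column is zero by definition.* That follows only from the literal reading. The text also allows sites to flag tamoxifen events.
- *Tamoxifen's thromboembolic risk escapes 24-hour reporting.* Serious events are SAEs in either arm (Protocol 7.1.1). Medically significant events must be reported as SAEs (7.1.1.3). SAEs carry the same 24-hour clock (7.2.1). Even on the narrow reading, only tamoxifen events that are neither serious nor medically significant lose that route.
- *Such events are followed to outcome in one arm only.* Protocol 7.2 requires follow-up of every adverse event until resolution, stability, loss to follow-up or withdrawal of consent, in both arms.
- *A formal randomised comparison is invalidated.* None is planned for AESIs.

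What the reply does not remove is the undefined scope. The possibility that some sites flag tamoxifen events makes the count less predictable, not more comparable. That other tables hold the events is a reason why the repair is easy, not a reason to publish an AESI row that cannot be interpreted.

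**Conclusion.** The point holds as a defect of scope and derivation. The AESI list is labelled for one drug, its application to the other is not stated, and the plan presents AESIs by arm without saying how the flag is made. As written, the tamoxifen count is either empty or dependent on site interpretation in an open-label trial, so the per-arm AESI counts are not comparable.

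The size cannot be derived from the documents. The 2% to 10% range and the flagging fractions are assumptions that show scale only: at most a few patients per arm. The primary endpoint, the SAE data and the general adverse event tables are unaffected. This is a cheap improvement to one planned safety row and not a threat to the trial's main conclusion.

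**What to change.** **SAP 2.5 and 4.5.2.** Define the AESI flag and derive it by the same criteria in both arms: a pre-specified set of MedDRA preferred terms with the recorded CTCAE grade, plus laboratory values for the Hy's Law, transaminase and creatinine items. Apply it to all patients, including those already treated. Do not use site AESI flags for the between-arm table; if they are shown, list them separately. Note that the infectious-agent item rests on what the investigator recorded. Enter the derivation in SAP section 6. This works even if enrolment has finished.

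**Protocol 7.1.2.** Reconcile the heading with the list by stating whether the list and its 24-hour clock cover both investigational products. The content of any tamoxifen list, and which of its events are expedited, is for the sponsor to decide.

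**Cost.** A few sentences and slight extra programming. If the sponsor extends the list to tamoxifen, sites will file a few more expedited forms.
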